4. STUDY POPULATION

4.1. Inclusion Criteria – Double-Blind Treatment Period

Subjects must meet ALL of the following inclusion criteria to be eligible for enrollment into the study:

1. Men or women between ≥ 18 and ≤ 70 years of age at the time of informed consent.
2. Chronic AD, defined by Hanifin and Rajka criteria ([REDACTED]), that has been present for at least 1 year prior to the Screening Visit.
3. EASI ≥ 12 at the Screening Visit and ≥ 16 at the Baseline Visit.
4. vIGA score ≥ 3 (on the 0 to 4 vIGA scale, in which 3 = moderate and 4 = severe) involvement at the Screening and Baseline visits.
5. BSA $\geq 10\%$ of AD involvement at the Screening and Baseline visits.
6. Recent history (within 6 months prior to the Screening Visit) of inadequate response to treatment with topical medications, or when topical treatments are otherwise medically inadvisable (eg, because of important side effects or safety risks), which can be documented by medical records or by the history provided to the investigator by the subject despite optimized skin care (ie, avoidance of irritants, use of emollients).
7. Willing to apply a dose of topical emollient/moisturizer at least once daily for ≥ 1 week prior to the Baseline Visit and willing to continue daily application over the course of the study without change (ie, type, frequency, application).
8. Willing and able to comply with all clinic visits and study-related procedures and understand and complete study-related questionnaires.
9. Provide signed informed consent prior to conducting any procedures.

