This plan will cover the analyses for: 1) the primary database lock after the completion of the Double-Blind (DB) Treatment Period; 2) the final database lock after the completion of the Open-Label Extension (OLE) Period. The plan will be finalized before the time of primary database lock and treatment unblinding. After that, the SAP may be amended to accommodate ad hoc analyses before the final database lock. Ad hoc analyses will be labeled as such on the output and identified in the Clinical Study Report.

2. Protocol Objectives

A. Primary Objective

To assess the efficacy of etrasimod monotherapy (1 or 2 mg) in subjects with moderate to severe atopic dermatitis (AD) during the DB Treatment Period.

B. Safety Objective

To assess the safety and tolerability of etrasimod monotherapy (1 or 2 mg) in subjects with moderate to severe AD during the DB Treatment Period.

C. Open Label Extension Objective

To assess the long-term safety, tolerability, and efficacy of etrasimod monotherapy (2 mg) in subjects with moderate to severe AD.

3. Study Endpoints

A. Primary Efficacy Endpoint

Percent change in Eczema Area and Severity Index (EASI) from Baseline to Week 12.

[REDACTED]

B. Key Secondary Efficacy Endpoints

- Proportion of subjects achieving EASI-75, defined as a 75% reduction of EASI from Baseline to Week 12.
- Proportion of subjects achieving a validated Investigator’s Global Assessment (vIGA) of 0 or 1 (on a 5-point scale) and a reduction from Baseline of ≥ 2 points at Week 12.

C. Secondary Efficacy Endpoints

- Percent change in weekly peak pruritus numeric rating scale (NRS) from an itch daily diary from Baseline to Week 12.
- Proportion of subjects with improvement (reduction) in weekly peak pruritus NRS ≥ 3 from an itch daily diary from Baseline to Week 12.
- Proportion of subjects achieving EASI-50, defined as a $\geq 50\%$ reduction of EASI from Baseline to Week 12.
- Proportion of subjects achieving EASI-90, defined as a $\geq 90\%$ reduction of EASI from Baseline to Week 12.
- Change and percentage change in percent body surface area (BSA) AD involvement total and for each body region from Baseline to Week 12.

D. Exploratory Efficacy Endpoints

- Change in Dermatology Life Quality Index (DLQI) from Baseline to Week 12.
- Change in Patient Oriented Eczema Measure (POEM) from Baseline to Week 12.
- Percent change in SCORing Atopic Dermatitis (SCORAD), total and by symptom (severity, and subjective symptoms), from Baseline to Week 12.

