Statistical analysis will be performed following IQVIA Biotech standard operating procedures and on the IQVIA Biotech computer network. All statistical analysis will be performed using SAS Version 9.4 with program code prepared specifically for the project by qualified IQVIA Biotech statisticians and SAS programmers.

All observed and derived variables (e.g., change from baseline, percentage change from baseline, and response status) that are analyzed or summarized will be listed by subject. Descriptive statistics will provide an overview of the efficacy and safety results. For categorical parameters, the number and percentage of subjects in each category will be presented. For continuous parameters, descriptive statistics will include number of subjects, mean, SD median, minimum, and maximum.

B. Definition of Baseline and Study Day

Study day will be defined separately for the DB Treatment Period and OLE Period. For all subjects, Day 1 is the date of first study drug administration in the DB Treatment Period. This will be referred to as the **Overall Day 1**. For those enrolling into the OLE Period, an **OLE Day 1** will be additionally defined as the date of the first study drug administration in the OLE Period at Week 16.

Study day will be calculated relative to the date of Overall Day 1.

Similarly, Baseline will be defined separately for DB Treatment Period and OLE Period as follows:

[figure not shown]
- **DB Treatment Period:** baseline will be defined as the last available measurement prior to the first dose of the study drug in DB Treatment Period. Specifically, for vital signs (resting heart rate (HR), blood pressure (BP), body temperature, and respiratory rate) and [REDACTED], the Day 1 pre-randomization assessments will be used as baseline measurements. The lowest pre-dose HR measurement will be used for comparison to the post-dose HR measurement. This will be referred to as the **DB baseline**.

[figure not shown]
- OLE Period: for those enrolling into the OLE Period, an **OLE baseline** will be additionally defined as the last pre-dose measurement at Week 16 at Week 16.

Change from baseline is defined for both DB Treatment Period and OLE Period as the post-baseline value minus the baseline value unless otherwise specified. Percent change from baseline is calculated as follows: Percent change = (Change from baseline / Baseline) x 100.

C. Analysis Visit Window

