A. Disposition

Subject disposition in the whole study (DB Treatment Period and OLE Period) will be summarized using frequency counts and percentages, including: subjects

who were screened, randomized, enrolled into OLE Period, completed treatment in DB Treatment Period, completed treatment in the DB Treatment Period and OLE Period, discontinued treatment (overall and by reason of discontinuation) and discontinued study (overall and by reason of discontinuation). Screen failures will be summarized for overall only and by reason of screen failure.

B. Analysis Set Inclusions

The numbers and percentages of FAS subjects included in SAF, any mFAS, PPS, TCS, [REDACTED] will be presented for each treatment group and overall. Reasons for exclusion from the PPS will be summarized.

C. Protocol Deviations

The major protocol deviations will be summarized for each category by treatment group and all protocol deviations will be presented in a by-subject listing. The protocol deviations that lead to subjects being excluded from PPS will also be presented in the listing.

8. Efficacy Analyses

A. Efficacy Outcomes

- **EASI** is a validated scoring system that grades the severity and extent of AD. It is a composite index with scores ranging from 0 to 72. Percent change (0 -100) in EASI from Baseline to Week 12 is the primary efficacy endpoint.
- **vIGA** is a 5-point scale to measure disease severity: 0 = clear; 1 = almost clear; 2 = mild; 3 = moderate; and 4 = severe.
- **SCORAD** is a validated measure of the extent and severity of AD. There are 3 components to the assessment: A = extent or affected BSA, B = severity, and C = subjective symptoms. BSA is described below in BSA AD section. The severity of 6 specific symptoms of AD (redness, swelling, oozing/crusting, excoriation, skin thickening/lichenification dryness) is assessed using the following scale: none (0), mild (1), moderate (2), or severe (3) (for a maximum of 18 total points, assigned as “B” in the overall SCORAD calculation). Subjective assessment of itch and sleeplessness is recorded for each symptom by the subject or relative on a Visual Analogue Scale, where 0 is no itch (or sleeplessness) and 10 is the worst imaginable itch (or sleeplessness), with a maximum possible score of 20. This parameter is assigned as “C” in the overall SCORAD calculation. The SCORAD total score is calculated as: $A/5 + 7B/2 + C$ where the maximum is 103.

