- **Pruritus NRS** is a simple assessment tool of the intensity of pruritus (itch) from 0 to 10 with 0 being “no itch” and 10 being “the worst itch imaginable.” Both maximum/peak and average NRS scores will be assessed.

In a daily diary, subjects are asked to rate their worst itch and itch on average over the previous 24 hours. The weekly average NRS (peak and average) will be analyzed as efficacy endpoints, and derived as per the following schedule and rule:

- For DB Treatment Period: Baseline (Day 1), Week 1 (Day 2 to 8), Week 2 (Day 9 to 15), Week 3 (Day 16 to 22)...Week 12 (Day 79 to 85)... and Week 16 (Day 107 to Day 113 or Day of Week 16 visit whichever comes first for subjects enrolled into OLE Period).
- For OLE Period: Week 17 (Day of week 16 visit +1 to Day 120), Week 18 (Day 121 to 127), Week 19 (Day 128 to 134)...Week 28 (Day 191 +).
- Subjects must complete at least 3 NRS entries to calculate the weekly average. The weekly average will be considered missing if more than 4 entries are missing for that weekly interval. The baseline for the analysis of diary data is Day 1.

At each scheduled office visit, the subject is asked to rate their worst itch and itch on average in the past 7 days and these are recorded as office based peak and average NRS.

- **BSA AD** will be assessed for each region of the body and combined. The region percent affected BSA is the affected percentage (0-100) at each body region. The total percent affected BSA is the sum of multiplying region percent affected BSA by the multiplication factor with a maximum of 100.

Body Region	Multiplication Factor
Head and Neck	9%
Upper Limbs (right)	9%
Upper Limbs (left)	9%
Lower Limbs (right)	18%
Lower Limbs (left)	18%
Anterior Trunk	18%
Back	18%
Genitals	1%

- **PGA** includes 2 questions **for wellness and appearance**. Subjects will rate their overall well-being based on a 5-point Likert scale from poor to excellent. Response choices are: ‘Poor’, ‘Fair’, ‘Good’, ‘Very Good,’ or ‘Excellent’.

- **POEM** consists of 7 questions asking patients to rank how many days over the past 7 days they have experienced specific AD-related symptoms. Each of the seven questions carries equal weight and is scored from 0 to 4 as follows:

No days	Scored 0
1-2 days	Scored 1
3-4 days	Scored 2
5-6 days	Scored 3
Every day	Scored 4

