- Longitudinal continuous variables (percent change in weekly peak pruritus NRS, change and percentage change in %BSA) measured at visits (weeks) up to Week 12 will be analyzed with a MMRM model based on FAS using observed data. The MMRM model will include treatment group, visit (week), and interaction of treatment-by-visit (week) as factors, and baseline measure and randomization stratification factors as covariates. An unstructured covariance matrix will be specified for the MMRM model. If the model does not converge using an unstructured covariance matrix, an auto-regressive AR(1) structure will be tested. If AR(1) fails to converge, a compound symmetric structure will be used. LS means at visit (week) and LS mean differences at visit (week) between treatment group with p-values and corresponding 95% CIs will be reported.
- Dichotomous measures (weekly peak NRS ≥ 3 reduction, EASI-50, and EASI-90) at Week 12 will be analyzed in the same way as for the key secondary endpoints based on FAS with CMH method adjusted for randomization stratification factors of baseline vIGA score (3 versus 4) and region [REDACTED]. Missing data (including those after use of rescue medication) will be handled by NRI method. The number, percentage of subjects achieving the goal and Clopper-Pearson exact 95% confidence intervals will be reported. The differences in proportion between treatment groups, along with p-values and the 95% CIs will also be reported. Weekly peak NRS ≥ 3 reduction will be assessed among the subset of subjects whose baseline peak NRS is ≥ 3 .

Sensitivity analyses will be performed in the PPS and TCS using observed data.

E. Exploratory Efficacy Outcome Analysis

Below exploratory endpoints will be analyzed in a similar manner as the secondary continuous variables with the MMRM model based on FAS using observed data.

- Change in DLQI from Baseline to Week 12.
- Change in POEM from Baseline to Week 12.
- Percent change in SCORAD total and individual symptom scores from Baseline to Week 12.

The primary and sensitivity analysis for all efficacy endpoints are summarized in **Table 3**.

Table 3 Summary of Efficacy Analyses

Efficacy Endpoint	Primary Analysis	Sensitivity Analysis
DB Treatment Period		
Primary		

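### In the readable double-blind plan, individual SCORAD symptoms are analysed only as percent change, which is undefined for a subject whose baseline score is 0

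*SAP*

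**What the plan says.** **SCORAD.** SAP 3.D lists "Percent change in SCORing Atopic Dermatitis (SCORAD), total and by symptom (severity, and subjective symptoms), from Baseline to Week 12". SAP 8.E repeats it as "Percent change in SCORAD total and individual symptom scores from Baseline to Week 12" and assigns it to the MMRM used for the continuous secondary endpoints, on the FAS with observed data. Table 3 itemises the total, six severity symptoms and two subjective symptoms, and plans no sensitivity analysis. SAP 8.A scores each severity symptom from 0 (none) to 3 and each subjective symptom (itch, sleeplessness) from 0 to 10. SAP 5.H rules out imputation for exploratory endpoints.

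**Formula.** SAP 5.B applies "Percent change = (Change from baseline / Baseline) x 100" generally. The readable text has no rule for a baseline of 0.

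**BSA.** SAP 3.C lists "Change and percentage change in percent body surface area (BSA) AD involvement total and for each body region from Baseline to Week 12", and Table 3 confirms both scales for the total and eight regions. SAP 8.A adds: "The region percent affected BSA is the affected percentage (0-100) at each body region" and "The total percent affected BSA is the sum of multiplying region percent affected BSA by the multiplication factor with a maximum of 100".

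**Eligibility.** Protocol 4.1 requires, at Baseline, total BSA of at least 10%, EASI of at least 16 and vIGA of at least 3. No readable criterion sets a minimum for a single SCORAD symptom or a single body region.

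**The concern.** Baseline is the denominator at every visit. A subject who starts at 0 on a symptom therefore has no percent change at any visit and contributes no record to that symptom's MMRM. The table would still carry the FAS label, while each symptom rests on a different subset of subjects with that symptom at baseline. A symptom that first appears during treatment cannot show up in its own analysis. For those who remain, a short ordinal scale turned into percentages gives the same one-point step very different weight.

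The same formula applies to regional BSA, but there the SAP also plans absolute change, which is defined at 0. For the SCORAD symptoms the readable double-blind plan has no such companion analysis. At stake is how far the symptom-level exploratory results can be interpreted, including which symptoms improve and whether any emerge.

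**Working it through.** The documents state no figure to reproduce here. The check applies the SAP's formula to the SAP's scales.

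**1. Severity item (0–3).** Percent change = 100 × (Week 12 − baseline) / baseline:

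| Baseline | Week 12 = 0 | 1 | 2 | 3 |
|---|---|---|---|---|
| 0 | undefined | undefined | undefined | undefined |
| 1 | -100% | 0% | +100% | +200% |
| 2 | -100% | -50% | 0% | +50% |
| 3 | -100% | -66.7% | -33.3% | 0% |

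A one-point improvement is -100% from 1, -50% from 2 and -33.3% from 3. Worsening from 0 to 3, the largest possible, has no value. On a 0–10 item, a one-point improvement is -100% from 1 and -10% from 10.

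**2. Can eligible subjects start at 0?** EASI grades erythema, thickness, excoriation and lichenification (Protocol 10.3.1). The vIGA descriptors rest on erythema and papulation (Protocol 10.3.3). Neither requires a non-zero score for oozing/crusting, dryness, itch or sleeplessness. Zero is therefore possible; how common it is, the documents do not say.

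**3. Subjects lost, by assumed zero-baseline share.** Remaining = 40 × (1 − share): 10% leaves 36, 20% leaves 32, 30% leaves 28, 50% leaves 20 per arm.

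**4. What the percent scale misses (assumed values, simple means rather than a fitted MMRM).** One arm of 40. Subjects with the symptom go from 2 to 1, and a quarter of those at 0 go to 3.

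| Share at 0 | Mean percent change | Mean absolute change | Newly symptomatic, uncounted in percent |
|---|---|---|---|
| 10% | -50% (n = 36) | (36 × -1 + 1 × 3)/40 = -0.825 | 1 |
| 20% | -50% (n = 32) | (32 × -1 + 2 × 3)/40 = -0.65 | 2 |
| 50% | -50% (n = 20) | (20 × -1 + 5 × 3)/40 = -0.125 | 5 |

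The percent result does not move. The absolute result does.

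**5. SCORAD total.** Total = A/5 + 7B/2 + C, where A is the affected BSA. With BSA of at least 10%, the total is at least 10/5 = 2 at baseline, so its percent change is always defined.

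**6. BSA.** The regional factors sum to 9+9+9+18+18+18+18+1 = 100. On the BSA criterion alone, any one region with factor 18% can reach 10%, so up to seven of eight regions could be 0. Regional absolute change is still defined, and total BSA counts new sites. As an illustration of the formula, take back 60 to 30%, head and neck 0 to 20%, genitals 0 to 50%. Baseline total = 0.18 × 60 = 10.8. Week 12 total = 0.18 × 30 + 0.09 × 20 + 0.01 × 50 = 7.7. The change is -3.1 points, or 100 × -3.1/10.8 = -28.7%, against -50% for the back alone. The new involvement is visible.

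**The case against.** - **BSA is already handled.** A reader might infer that new disease in previously clear body regions is lost. It is not: absolute change per region is planned in the same sentence as percent change, and the total includes every region. This objection stands in full. Only the regional percent-change tables omit subjects with a clear region.
- **Zero baselines may be rare.** A reader might infer from the 10% BSA floor that zeros are common. The documents give no baseline distribution, and EASI of at least 16 and vIGA of at least 3 also apply, so seven clear regions is a bound on one criterion and not a typical subject. This stands.
- **The subset is still randomised.** A reader might infer bias from comparing unrandomised groups. A subset defined by a pre-dose value is a baseline subgroup, and the arms within it remain a randomised comparison. SAP 8.D does this openly for the NRS response, restricting it to baseline peak NRS of at least 3. This stands against any claim of bias. It also shows that the SAP states such a restriction when it intends one, and none is stated here.
- **Other SCORAD information exists.** The total includes every symptom, SAP 11.A uses absolute change in the total, itch has its own NRS endpoints, and observed values are listed by subject (SAP 5.A). This softens the gap, but none of it gives a symptom-level summary that includes subjects who start at 0.
- **Redaction.** Text after the SCORAD bullet in 3.D and rows of Table 3 are blacked out, so one cannot say that no other symptom analysis exists. This stands, and the point is limited to the readable plan.
- **Unequal weighting is a property of any percent scale.** True, but it is extreme on a 0–3 item, where a single point can be the whole range below baseline.

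**Conclusion.** The point holds for the eight individual SCORAD symptoms. As readable, they are analysed in the double-blind period by percent change only, which is undefined at a baseline of 0 and uneven on a 0–3 scale. Applied as written, the FAS label would then cover a smaller, symptom-specific subset. That subjects drop out is a consequence of the formula and the observed-data model; the SAP does not state an exclusion. The number affected is unknown: 4 to 20 of 40 per arm under an assumed 10% to 50% share at 0.

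For BSA regions the point reduces to labelling, since absolute change already captures new involvement.

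Severity is low. The symptom analyses are exploratory, SAP 5.F plans no formal testing strategy, and the primary and key secondary endpoints are untouched (baseline EASI is at least 16, so its percent change is always defined).

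**What to change.** 1. In SAP 3.D, 8.E and Table 3, analyse the six severity and two subjective SCORAD symptoms as absolute change from baseline, in the same MMRM with the baseline value as covariate, including subjects with baseline 0. Keep percent change for SCORAD total.
2. In SAP 3.C, 8.D and Table 3, name absolute change as the main result for the eight BSA regions. If regional percent change is kept, label it as restricted to subjects with baseline above 0 and report the number excluded per arm.
3. In SAP 5.B, state that percent change is not calculated when baseline is 0.

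The cost is SAP wording and a change of response variable in the symptom tables. No extra data are needed, and the results for SCORAD total, total BSA, and the primary and key secondary endpoints do not change.

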9.2.4. Double-Blind Treatment Period Safety Follow-Up Visit

Subjects who complete the Double-Blind Treatment Period will return for a Safety Follow-Up Visit 4 weeks after the last dose of study treatment (Week 16). Visit assessments are detailed in the [REDACTED].

Subjects who terminate the study treatment early in the Double-Blind Treatment Period, should have an EoT Visit (Section 9.3) and a Safety Follow-Up Visit 4 weeks after the last dose of study treatment.

For subjects that have discontinued study treatment prior to Week 12 or are determined ineligible for the Open-Label Extension Period (Section 9.2.5), Week 16 will be the End of Study Visit (Section 9.4). Whenever possible, visits should be scheduled on the Weeks designated in the [REDACTED].

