Efficacy and safety endpoints will be analyzed according to their windowed visits defined by actual overall study day (i.e. calculated relative to first dose date in the DB Treatment Period). If more than one visit occurs within a single visit window, then the analysis will take the one closest to the target day. If the 2 visits are equidistant from the target day, the later visit will be used. Some efficacy or safety data are not scheduled to be assessed at each post-baseline visit. If the assessment date is not in the analysis visit window, the analysis will take the post-baseline scheduled visit closest to the assessment date. If there are 2 scheduled visits equidistant from the assessment date, the later visit will be used. The below table provides details of each analysis visit window.

D. Covariate Adjustment in Primary Analysis

The primary efficacy analyses will adjust for baseline EASI score, baseline vIGA score (3 versus 4) and region [REDACTED]. Key secondary analyses will adjust for baseline vIGA score (3 versus 4) and region [REDACTED] as described in Section 8 Efficacy Analyses below.

E. Interim Analyses

No formal interim analysis of efficacy is planned. Periodic blinded assessments may be conducted to assess the assumption regarding the SD of the percentage change in EASI from Baseline to Week 12. The planned sample size will not be reduced as a result of the SD assessments.

F. Multiple Comparisons and Multiplicity

For DB Treatment Period: no formal testing strategy or adjustments of the Type I error will be employed for the primary and key secondary endpoints. Estimates and confidence intervals (CIs) for treatment groups and from pairwise comparisons will be reported in an exploratory manner.

[figure not shown]
For the OLE Period: no formal statistical testing will be performed. Only descriptive statistics will be provided.

G. Analysis Sets

The following analysis sets will be defined for the DB Treatment Period and OLE Period separately:

Table 2 Analysis Sets

Analysis Set	Description
DB Treatment Period	
Full Analysis Set (FAS)	The FAS includes all randomized subjects, irrespective of whether they received any study treatment.

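### SAP 5.B, 5.C and 8.A do not count open-label extension time from one anchor, so the itch diary around Week 16 has unassigned days and a Week 17 of variable length

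*SAP*

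**What the plan says.** SAP 5.B opens with "Study day will be defined separately for the DB Treatment Period and OLE Period". It adds an OLE Day 1 that "will be additionally defined as the date of the first study drug administration in the OLE Period at Week 16". The computing rule that follows has one anchor only: "Study day will be calculated relative to the date of Overall Day 1".

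SAP 5.C applies that anchor to all efficacy and safety data, using "windowed visits defined by actual overall study day (i.e. calculated relative to first dose date in the DB Treatment Period"). When two visits share a window, the one nearer the target day is used, and the later one if they tie. For data outside a window: "If the assessment date is not in the analysis visit window, the analysis will take the post-baseline scheduled visit closest to the assessment date". The window table to which 5.C refers is not visible in the text available.

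For the diary, SAP 8.A sets "Week 16 (Day 107 to Day 113 or Day of Week 16 visit whichever comes first for subjects enrolled into OLE Period") and then "For OLE Period: Week 17 (Day of week 16 visit +1 to Day 120), Week 18 (Day 121 to 127"). A weekly mean needs at least 3 entries and is missing if more than 4 entries are missing.

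SAP 4.E allows 3 days either side at Week 16 and records later or earlier attendances as unscheduled visits. Protocol 9.2.4 times the same visit from the end of dosing: "Safety Follow-Up Visit 4 weeks after the last dose of study treatment (Week 16"). The first open-label dose belongs to that visit, so its study day differs between subjects.

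**The concern.** The two study-day statements in SAP 5.B cannot both be applied as written, and no visible window or diary rule uses OLE Day 1 by name. In 8.A the consequence is concrete. One boundary (the start of Week 17) follows the subject's actual Week 16 visit, while its neighbours (the latest end of Week 16 and the end of Week 17) are fixed days from the first double-blind dose. Unless the visit falls exactly on Day 113, the intervals do not fit together.

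At stake are the extension summaries by visit in SAP 8.F, which include the pruritus NRS. The first extension week is the first exposure to etrasimod for former placebo subjects and a re-start after about 4 weeks off drug for the others. Under the present rules that week can be short, long or always missing, depending only on the day of the Week 16 visit.

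**Working it through.** **Inputs.** Diary intervals, the 3-entry minimum and the rule of more than 4 missing: SAP 8.A. Week 16 tolerance of 3 days: SAP 4.E. Nearest-visit and tie rules: SAP 5.C. Let V be the day of the Week 16 visit, taken as the day of the first OLE dose.

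**The plan's own calendar.** Week k = Day 7k − 5 to Day 7k + 1 reproduces the stated intervals for Weeks 1, 2, 3, 12, 18 and 19, the basic Week 16 interval (Day 107 to 113), the end of Week 17 (7 × 17 + 1 = 120) and the start of Week 28 (7 × 28 − 5 = 191). The exceptions are the two boundaries tied to the visit.

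**Diary.** For V up to 120:
- Week 16 runs from Day 107 to the smaller of 113 and V.
- Unassigned days run from Day 114 to V; their number is V − 113 if positive.
- Week 17 runs from V + 1 to 120; its length is 120 − V.

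| V | Week 16 days | Days in no week | Week 17 days |
|---|---|---|---|
| 110 | 4 | 0 | 10 |
| 113 | 7 | 0 | 7 |
| 114 | 7 | 1 | 6 |
| 115 | 7 | 2 | 5 |
| 116 | 7 | 3 | 4 |
| 117 | 7 | 4 | 3 |
| 118 | 7 | 5 | 2 |
| 119 | 7 | 6 | 1 |
| 120 | 7 | 7 | 0 |

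Rows 110 to 116 lie inside the allowed window (113 ± 3). At V = 117 all 3 possible entries are needed. From V = 118 the minimum cannot be met.

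**Entry rules in a 10-day week.** With n entries, the first rule allows a mean if n ≥ 3. The second makes it missing if 10 − n > 4, that is n ≤ 5. The rules contradict each other for n = 3, 4 and 5.

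**Off-drug diary days in an OLE week.** Week 17 starts after the visit, so it holds none. Week 18 is fixed at Day 121 to 127 and takes in off-drug days only if V is 121 or later, at least 8 days late.

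**Clinic visits, assuming midpoint windows.** The targets are Day 113 and Day 120, with midpoint 116.5. A pre-dose record on Day 117 or later (at least 4 days late) then falls in Week 17. Whether it is used depends on the next visit:
- V = 117 is 3 days from target. Any visit on Days 118 to 123 displaces it, because Day 123 ties and the later visit wins. A visit one week later, on Day 124, is nearer to Day 127 (Week 18), so the pre-dose record stays as Week 17.
- V = 118 is 2 days from target. Visits on Days 119 to 122 displace it. A visit on Day 123, inside the Week 17 tolerance, is 3 days away and loses.

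Where the pre-dose record is kept, it is also the OLE baseline under 5.B, so its Week 17 change from OLE baseline is zero by construction.

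**The case against.** The strongest reply is that counting from double-blind Day 1 is harmless in itself: the calendar of 7k − 5 to 7k + 1 is continuous and leaves no gap. That is correct. The gap comes from joining a visit-based boundary to fixed ones in 8.A. A reader might blame the study-day sentence in 5.B alone, but the text does not support that.

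Some stronger readings also go too far.
- **Off-drug clinic data routinely counted as on-treatment.** This needs a Week 16 visit at least 4 days late and no Week 17 visit that displaces it, and it assumes midpoint windows in a table that cannot be seen.
- **Day 119 as a compliant visit.** One could add a last dose on Day 88 (Week 12 at + 3 days), 28 days, and 3 more days. SAP 4.E schedules Week 16 from Baseline/Day 1 within 3 days, so Day 116 (88 + 28) already uses that tolerance and the last 3 days count it twice.
- **An objective defined by time on open-label drug.** SAP 2.C and Protocol section 2 speak of long-term safety, tolerability and efficacy. Early safety is also covered elsewhere: vital signs around the Week 16 dose (SAP 9.E), exposure by period (9.A) and adverse events by period (9.C).
- **The open-ended Week 28 diary interval.** It has nothing to do with the anchor and is a separate matter.

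Finally, extension results are descriptive only (SAP 5.F, Protocol 11.9). That limits the importance of the point. It does not remove the unassigned days, which arise with visits that are fully on schedule under SAP 4.E.

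**Conclusion.** The point holds in limited form. The statements in SAP 5.B need to be reconciled, and the 8.A diary rules fail within the permitted visit window: up to 3 days in no week, a Week 17 of 4 to 10 days, and contradictory entry rules when it is 10 days long. These results need only the printed intervals and the assumption that the first OLE dose is given on the day of the Week 16 visit.

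The loss of the Week 17 itch mean from Day 118 also follows directly, but only for visits outside the window. Such visits are kept as unscheduled, and SAP 11.B expects some visits to be altered or missed because of COVID-19. The documents give no frequency. The clinic mislabelling is conditional on the unseen window table.

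The effect is confined to descriptive extension summaries, mainly Weeks 16 to 18. The Week 12 primary and key secondary analyses are untouched.

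**What to change.** In SAP 5.B, 5.C and 8.A:
- Window every assessment after the first OLE dose by OLE study day, with OLE Day 1 as the date of that dose.
- Set diary Week 17 to OLE Days 2 to 8, Week 18 to OLE Days 9 to 15, and so on. In overall days Week 17 is V + 1 to V + 7 and Week 18 is V + 8 to V + 14, so each has 7 days and no off-drug days for any V.
- Assign every record before the first OLE dose to Week 16 or OLE baseline, never to an OLE week.
- Keep the Week 16 diary interval starting at Day 107. A 7-day interval ending at the visit looks tidier, but Week 15 is Day 100 to 106: a Day 116 visit would leave Days 107 to 109 unassigned, and a Day 110 visit would count Days 104 to 106 twice.
- State that days from Day 114 to the visit are pre-OLE and off drug, and either add them to Week 16 or exclude them explicitly. If they are added, Week 16 has 10 days for a Day 116 visit (116 − 106), so a single entry rule must be chosen for intervals that are not 7 days long.

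One consequence should be accepted openly: the analysis week may differ from the nominal visit. After a Day 110 start, a Day 123 visit is OLE Day 14, nearer to Week 18 (OLE Day 15) than to Week 17 (OLE Day 8).

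The cost is SAP wording and a change of anchor date in programming. OLE Day 1 is already defined and no new data are needed.
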